9.1 Harms

We will collect data on death and secondary hospitalisations as part of the primary outcome. Given the low-risk nature of the intervention, the pragmatic nature of the trial, and that deaths and hospitalisations are, unfortunately, expected in this population, the DMC will review summarised rates of adverse events will be summarized by intervention and control arms and included in a report for the DMC to review. If a considerable difference (of >30%) is found, we will conduct a more in-depth evaluation (through analysis of clinical data, and collection of additional case note data from hospitals if required) of whether deaths or secondary hospitalisations are attributable to the intervention will be conducted.

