4.2 Intervention adherence and Protocol Deviations

While in India pulse oximeter was indicated for all children, in Tanzania, pulse oximeter was indicated for all young infants and for older children with cough/difficult breathing or red/yellow IMCI classification. Cough/difficulty breathing and red/yellow IMCI classification are defined two ways, based on signs and symptoms as reported by the caregiver pre-consultation or on diagnosis made by the healthcare provider during the consultation. These definitions are detailed in a separate document and both will be used, separately, to assess intervention adherence.

Adherence will be evaluated separately for the two intervention arms on the basis of pulse oximeter and CDSA use when indicated.

- ξ Pulse oximetry adherence will be evaluated primarily using information on SpO₂ values from clinical records. Pulse oximetry will be considered used if the RA has found any SpO₂ recording (value readable or unreadable). Pulse oximetry will be considered not used if the RA did not find any recorded SpO₂. Adherence will be additionally evaluated based on pulse oximetry use as reported by the caregivers.
- ξ CDSA adherence will be evaluated by comparing the number of children enrolled and the number of children recorded into the CDSA database. These data will be used to explore further and in more details adherence to the CDSA, but outside the scope of this SAP and it will be detailed in a separate document.

Adherence will be reported overall and weekly by facility.

The following information will be summarised by arm to evaluate deviations to the study protocol:

- ξ Number and percentage of caregivers for which no Day 7 follow-up was attempted.
- ξ Number and percentage of caregivers for which no Day 28 follow-up was attempted.

More general deviations will be recorded by the study team in a study deviation log and categorised into minor and major.

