4.3 Analysis Populations

All analyses will follow the intention to treat (ITT) principle, retaining facilities and participants in their initially randomised groups irrespective of the intervention received or any protocol violations. However, clusters provided from the start of the trial with a different intervention package than the one they were randomised to will be analysed according to the arm of the intervention they delivered.

A complete case set will also be defined, including only participants whose follow-up information are available (i.e. at least one follow-up was conducted). Analysis of the primary outcomes will be performed on both the ITT and the complete case set for final analysis and analyses for the DMC review.

No safety set will be defined but safety information will be reported overall and by use of intervention as defined in section 4.2.

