6.5 Harms

Safety of the interventions will be evaluated in terms of deaths and secondary hospitalisations that occurred throughout the course of the study. Deaths, secondary hospitalisations and both combined will be reported as counts and percentages. Summary statistics will be presented separately for each intervention as outlined in Section 4.3.

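### The harms display in the SAP is grouped by use of the intervention, and deaths alone and secondary hospitalisations alone are not pre-specified by randomised arm

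*SAP*

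**What the plan says.** SAP 6.5 names the safety events: "Safety of the interventions will be evaluated in terms of deaths and secondary hospitalisations that occurred throughout the course of the study". They are to be shown as counts and percentages for deaths, for secondary hospitalisations and for both combined. On grouping, 6.5 says "Summary statistics will be presented separately for each intervention as outlined in Section 4.3". The rule in SAP 4.3 to which this leads is "No safety set will be defined but safety information will be reported overall and by use of intervention as defined in section 4.2".

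SAP 4.2 defines use from the record: "Pulse oximetry will be considered not used if the RA did not find any recorded" SpO2 value. It limits the assessment to the active arms: "Adherence will be evaluated separately for the two intervention arms on the basis of pulse oximeter and CDSA use when indicated". It also gives the country difference: "While in India pulse oximeter was indicated for all children, in Tanzania, pulse oximeter was indicated for all young infants", with older Tanzanian children added on the basis of respiratory symptoms or a yellow or red IMCI classification.

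Two other statements point towards the randomised arms. SAP 4.3 opens with "All analyses will follow the intention to treat (ITT) principle, retaining facilities and participants in their initially randomised groups". Protocol 9.1 says that "adverse events will be summarized by intervention and control arms" in a report for the DMC, with a closer evaluation if a difference above 30% appears.

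**The concern.** Whether oximetry was used is decided after randomisation, at the consultation, partly on the basis of how ill the child is. A harms table split on that variable does not compare randomised groups. It can show an excess of deaths among measured children when the device does nothing, and it has no defined control column.

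Separate death counts matter here. The composite leaves out admissions that follow a referral and occur within 24 hours, and Protocol 6.4.2 expects the intervention to increase exactly those admissions. If admissions move into that window, the composite can fall while deaths do not, so the composite alone cannot show what happened to deaths. Protocol 6.4.2 also makes a positive reading of the trial conditional on no sign of harm from the outcomes that are not significant. That judgement needs the components by arm.

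**Working it through.** **Where each safety quantity is given by randomised arm**

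- Death or secondary hospitalisation combined, Day 7 and Day 28: defined in SAP 6.1.2.1 and 6.1.2.2; described by arm and modelled against control under SAP 6.2.1 (the Day 28 model if numbers allow). Covered.
- Closed DMC report: by arm (SAP 6), but SAP 6.2.1 restricts DMC analyses to the two primary outcomes. The composite is covered; its components are not.
- Deaths alone and secondary hospitalisations alone: neither is in the outcome list of SAP 3.1.4. They appear as separate counts only in SAP 6.5, whose grouping is set by 4.3. Not stated by arm.

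The plan gives no figure for this point, so there is none to reproduce. What follows illustrates how far a used/not-used contrast can move with no intervention effect.

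**Inputs for Tanzania**

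- Overall risk R = 1.1% (control-arm severe complications, SAP 3.4). It cancels from the ratios.
- Share indicated s = 40%, 50% or 70%. This is an assumption, anchored on the 40–70% with cough or difficulty breathing in Protocol 6.3.
- Use if indicated u1 and if not indicated u0: 60%/20%, 80%/10% or 90%/5% (assumed).
- Risk of indicated relative to other children, k = 1.5, 2 or 3 (assumed).

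**Formulas**

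- r0 = R / (1 − s + s·k); r1 = k·r0
- Risk if used = [s·u1·r1 + (1 − s)·u0·r0] / [s·u1 + (1 − s)·u0]
- Risk if not used = [s·(1 − u1)·r1 + (1 − s)·(1 − u0)·r0] / [s·(1 − u1) + (1 − s)·(1 − u0)]

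**One case: s = 0.5, k = 2, u1 = 0.8, u0 = 0.1**

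- r0 = 1.1% / 1.5 = 0.733%; r1 = 1.467%
- Used: (0.40 × 1.467% + 0.05 × 0.733%) / 0.45 = 1.39%
- Not used: (0.10 × 1.467% + 0.45 × 0.733%) / 0.55 = 0.87%
- Ratio before rounding: 1.60
- If control children (one arm of three) are put with the not-used: (2/3 × 0.55 × 0.867% + 1/3 × 1.1%) / (2/3 × 0.55 + 1/3) = 0.978%, ratio 1.42
- By randomised arm: 1.1% against 1.1%, ratio 1.00

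**Range over all the inputs above**

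| k | Used / not used, intervention arms only | Control children added to not used |
|---|---|---|
| 1.5 | 1.13–1.42 | 1.10–1.32 |
| 2 | 1.22–1.80 | 1.16–1.58 |
| 3 | 1.32–2.52 | 1.23–1.99 |

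**India.** Every child was indicated, so the criteria create no contrast. If use is unrelated to severity the ratio is 1.00. If half the children carry three times the risk (assumed), use of 90% in the sicker and 70% in the others gives 1.169% / 0.825% = 1.42. Reversing the use rates gives 1.031% / 1.375% = 0.75. The sign is not determined by the documents.

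**The case against.** The strongest reply is that the randomised comparison exists already. The safety events are the parts of the Day 7 primary outcome, which is analysed by arm under ITT, and Protocol 9.1 itself says they are collected as part of that outcome. A reader might infer from SAP 4.3 that safety is reported by use in place of any by-arm comparison. The documents do not support that: the composite is compared by arm and the closed DMC report is by arm.

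Further parts of the reply stand. Protocol 9.1 concerns a report to the DMC and not the final harms table, and the DMC charter, which may say more, is not among the documents. The words on each intervention in SAP 6.5 could be read as arm, and the ITT sentence in 4.3 covers all analyses. The harms display is descriptive, with no test.

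A reader might also infer that measured children are generally sicker than unmeasured ones. That follows only for oximetry in Tanzania. It does not follow in India, nor for CDSA use, which Protocol 6.3 intends for all sick children. Even in Tanzania, SAP 4.2 assesses use when indicated, and within indicated children alone the illustration gives 1.00, although confounding by severity could remain.

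The reply does not remove the gap. The safety sentence in 4.3 is more specific than the ITT sentence before it. An arm reading of 6.5 still does not say that control is included. No by-arm analysis in the SAP separates deaths from secondary hospitalisations.

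**Conclusion.** The point holds in a limited form. As written, the harms display is overall and by a post-randomisation variable with no place for control children, and the separate counts of deaths and of secondary hospitalisations have no pre-specified comparison with control. The composite does have one.

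For oximetry in Tanzania, confounding by indication follows from the use criteria, which Protocol 6.3 says are meant to pick out the children most likely to be hypoxaemic. Its size is not known: the ratios of about 1.1 to 2.5 rest on assumed shares, use rates and relative risks, and no single value should be quoted as the expected bias. Several of these ratios exceed the 30% difference in Protocol 9.1 with no true effect. That threshold applies to the by-arm summary, so this comparison shows scale only; it is not a prediction that a review would be triggered.

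**What to change.** In SAP 4.3 and 6.5, state that deaths, secondary hospitalisations and both combined are tabulated by randomised arm, including control, separately for India and Tanzania, as the main safety display. Add the same table to the closed DMC report, and amend the limit to the two primary outcomes in SAP 6.2.1 to allow it.

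Keep the by-use table as a descriptive supplement, restricted to the intervention arms and split by whether use was indicated, as SAP 6.4 already does for the primary outcomes. Add a note that it is not a causal comparison.

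The data are already collected. The cost is a change of SAP wording and one extra table.

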5 STUDY POPULATION

5.1 Screening

No specific screening data will be captured, aside from those required to assess children's eligibility for the study (see section 5.2). The number of potential participants screened for the study will be presented in a CONSORT diagram by intervention arm.

5.2 Eligibility

The following are inclusion and exclusion criteria that determine facility and child eligibility:

Facility inclusion:

- ξ Consenting government-designated healthcare facilities within the selected geographical areas of each country
- ξ Providing curative primary care services for children 0 – 59 months of age
- ξ Oxygen available or referral mechanism in place with oxygen available at a higher level facility
- ξ Electricity available (from any source with continuous or intermittent supply)

Facility exclusion:

- ξ Attending to fewer than 20 sick children per month (based on the prior 12 month average)
- ξ Already using pulse oximetry as a routine part of outpatient-based consultations of children 0 – 59 months
- ξ Selected to be part of a major child health programmatic or research intervention during the study period likely to significantly affect the primary outcome
- ξ Inaccessible to the study team (e.g. due to weather conditions or security issues) for significant parts of the year.

Individual child inclusion:

- ξ Children 0 – 59 months for whom caregivers provide consent
- ξ Consulting for an illness, or reported to be unwell when attending for a routine visit (e.g. vaccination, growth or chronic disease monitoring)

Individual child exclusion:

- ξ Children in the immediate post-natal period or first day of life
- ξ Attending for a consultation related to trauma only (including new and follow-up presentations for burns, injuries, wounds)
- ξ Admitted within an inpatient part of the facility (including neonates delivered at the facility admitted with their mother)
- ξ Enrolled in the study within the preceding 28 days at any study facility

5.3 Recruitment

The number of participants enrolled will be presented in a CONSORT flowchart by intervention arm, together with the number of potential participants not recruited due to the child's eligibility

failure, caregiver's refusal to consent or caregiver being underage. Reasons for eligibility failure will be summarised.

Further enrolment figures will be presented by facility type, location and district and a graph will be produced showing monthly and cumulative recruitment.

Additionally, the percentage of eligible children (no. eligible/no. screened) and the percentage of recruited children (no. recruited/no. eligible) will be provided by intervention arm.

5.4 Withdrawal/Follow-up

The number of children for which follow-up was conducted will be presented in the CONSORT diagram by intervention arm for each of the scheduled assessment time point (Day 7 and Day 28). The number of children withdrawn in between follow-ups will also be summarised and reasons provided if available.

5.5 Baseline Participant Characteristics

Socio-demographic data of children enrolled and their caregivers will be summarised. Additional characteristics of interest, such as danger signs and symptoms as reported by the caregiver, will be presented as part of baseline summaries. Baseline data will be presented by intervention arm using median and associated interquartile range (IQR) if continuous and as counts and percentages if categorical. Summary statistics will be of non-missing values, with the number (%) of missing values given if data are not complete. Assessment will be made for baseline imbalances between the randomisation groups by visual inspection only and no formal testing will be performed.

For the baseline summaries, age of children will be reported as a continuous variable in months but also disaggregated in age groups. In the database, the age is estimated based on recommended standardised age disaggregation groups [6] with a different level of accuracy depending on the information provided by the caregiver. Based on age estimates, children are further categorised into young infants (<60 days) and children 60days-59 months. More details are provided in Appendix A.

6 ANALYSIS

Analyses will follow Consolidated Standards of Reporting Trials (CONSORT) guidelines [10] and will be performed and reported overall and by country.

Outcomes will be presented separately for young infants (<60 days) and older children (60 days-59 months), the malaria-related outcomes will be presented only on older children.

Results of interim analyses and DMC analyses will be presented overall in the open report and by intervention arm in the closed report.

6.1 Outcomes Definitions

This section presents general definitions, applicable to multiple outcomes, and a detailed definition of each primary and secondary outcome.

Outcomes definitions are grouped by topic rather than primary and secondary outcomes.

6.1.1 General definitions

Day 7 / Day 28 assessment

Day 7 / Day 28 assessment refers to information reported by the caregiver after Day 0 and recorded in Day 7 / Day 28 forms. Data collected as part of unscheduled visits are also integrated in these forms.

If multiple successful follow-up assessments for the same child are recorded within Day7 or Day28 databases, the most recent follow-up assessment within each database will be used. To limit potential recall bias, assessments conducted far beyond the expected follow-up time will be dropped. This will be 30 and 60 days from Day 0 for Day 7 and Day 28 respectively.

Death

A child will be considered deceased if, from Day 7 / Day 28 assessment, his/her status at the time of follow-up is “deceased”. In case of implausible death date (i.e. prior to enrolment date), death will be handled as follow:

- ξ if death date is recorded at Day7 follow-up, death will be assumed to be within 7 days of Day0
- ξ if death date is not recorded at Day7 follow-up but only at Day28 follow-up, death will be assumed to be after 7 days of Day0 but within 28 days.

Hospitalisation

A child will be considered hospitalised if, from Day 7 / Day 28 assessment, he/she went to a hospital, was admitted overnight or if his/her status at the time of follow-up is “hospitalised”. In case of implausible hospitalisation date (i.e. prior to enrolment date), hospitalisation will be handled as follow:

- ξ if hospitalisation date is recorded at Day7 follow-up, hospitalisation will be assumed to be within 7 days but after 24hrs of Day0
- ξ if hospitalisation date is not recorded at Day7 follow-up but only at Day28 follow-up, hospitalisation will be assumed to be after 7 days of Day0 but within 28 days.

Hospitalisation within 24hrs of Day0

For the purpose of primary analysis, a child will be considered admitted to hospital 24hrs of Day0 consultation if the date of hospitalisation is the same as Day0 date or is one day after Day0 date.

Referral

A child will be considered to be referred (either to a hospital or to an inpatient part of a larger primary healthcare facility) if, at Day0, the caregiver confirms that the child was urgently referred or the research assistant confirms that an urgent referral advice was recorded for the child. If urgency is unknown from both sources, referral will be assumed to be urgent.¹

Antibiotics

Antibiotics will be defined in accordance with the WHO antibiotic point prevalence survey (PPS) methodology [7, 8, 9] and therefore only antibacterials for systemic use will be taken into account.

¹ Urgency, as reported by the caregiver, was only collected in Tanzania. For India, urgent referrals will be defined based on the registry alone.

SpO₂ values

SpO₂ should be recorded during the Day0. For the outcomes, the following measures will be taken for spurious and missing SpO₂ values:

- If SpO₂ value is not available, the child will be assumed normoxaemic
- If $70 \leq \text{SpO}_2 < 90\%$, the child will be assumed (with accuracy) to have severe hypoxaemia
- If $40 \leq \text{SpO}_2 < 70\%$, the child will be assumed (with low accuracy) to have severe hypoxaemia
- If $\text{SpO}_2 < 40\%$, the value will be considered spurious (e.g. due to incorrect data entry) and treated as not available, i.e. the child will be assumed normoxaemic.

Additionally, a description of SpO₂ values distribution will be provided based on the following cut-offs:

- $95\% \leq \text{SpO}_2 < 100\%$
- $94\% \leq \text{SpO}_2 < 95\%$
- $92\% \leq \text{SpO}_2 < 94\%$
- $90\% \leq \text{SpO}_2 < 92\%$
- $70\% \leq \text{SpO}_2 < 90\%$ (severe hypoxaemia, accuracy)
- $40\% \leq \text{SpO}_2 < 70\%$ (severe hypoxaemia, but low accuracy)
- Spurious ($0\% \leq \text{SpO}_2 < 40\%$)
- Missing

In India, where three SpO₂ measures were collected, only the first one will be used.

Mild hypoxaemia

$92\% \leq \text{SpO}_2 < 94\%$

Moderate hypoxaemia

$90\% \leq \text{SpO}_2 < 92\%$

Severe hypoxaemia

$\text{SpO}_2 < 90\%$

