Caregivers will be offered several options for completing follow-ups at Day 7 and Day 28. Follow-up will be conducted remotely when possible. For caregivers who can provide a phone number at the day of enrolment, Day 7 and Day 28 follow-ups will be conducted by phone. If the initial phone call fails and the phone number is valid, at least three attempts will be made on subsequent three days at different times of the day to try to reach the caregiver. If the phone number is not valid, no other call attempts will be made and alternative follow-up options will be initiated if consented for. Except during the initial phone call, follow-up can be carried out with a caregiver other than the one who gave consent at the day of enrolment if this person is able to provide information about the child. For caregivers who cannot provide a phone number at the day of enrolment, community mechanisms will be relied on to arrange a call with the caregiver through a community focal person, e.g. a community health worker (CHW) or a community leader. To this aim, CHWs and community leaders in the targeted study areas will be asked for their consent to have their phone numbers shared with RAs in order to contact caregivers without a phone for their Day 7 and Day 28 follow-ups. Independently on whether they provided a phone number or not, caregivers will be given the alternative option to consent for in-person Day 7 follow-up that will have to be conducted as soon as possible after all remote attempts failed. In-person Day 7 follow-ups could be conducted either at the caregiver's household or another specified community location.. If Day 7 follow-up has been unsuccessful, Day 28 follow-up will still be attempted. During both Day 7 and Day 28 follow-ups, a structured questionnaire will be administered to assess the primary and secondary outcomes, including details of any government or private hospital admission. In case of non-recovery, if the child is still at home, the study team will advise the family to return to the PHC clinic for a follow-up consultation.

Additionally, visit information from government-designated hospital records will be collected retrospectively for children reported to have attended hospital by the caregiver at follow-up or referred at day 0 and lost to follow-up including clinical assessment on arrival (vital signs, admitting diagnosis), admission details (duration, if oxygen was administered, intensive care

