The validity of quantitative data will be ensured through data definitions and field restrictions in the electronic systems. Acceptable error rates in critical quantitative data will be established during the pilot phase and documented in the DMP. Pre-defined automated high-frequency checks will be performed including checks of completeness and indicators of other irregularities such as completion time. Reports will be shared with individual quantitative research assistants and their supervisors. In addition to reviewing automatically generated reports for their supervisees, supervisors will perform random accuracy checks of research data compared to available source data. In the pragmatic cluster RCT, quantitative research assistants responsible for the Day 7 call will be audited through random checks of phone logs and repeat phone calls. After confirmation that the study databases contain all expected data, an internal review will check their accuracy and quality. Once all the required data quality assurance and control have been completed and passed, the study databases will be "locked".

During the pilot phase, qualitative tools will be translated and back translated, and tested using cognitive interviewing to ensure questions asked are understood as intended and felt to be appropriate. Regular quality checks of transcriptions and translations will be conducted by the qualitative researcher in each country.

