6.1.2.8 Proportion of children cured at Day 7 follow-up

A child is defined as cured if he/she recovers from illness. A child will be counted in the numerator as cured if his/her status at the time of Day 7 follow-up is at home “well, completely recovered” and the follow-up date is within 7 days of Day 0, considering a + 3 days window (10th day included). The denominator will be all children recruited.

Children for whom no Day7 data are available or withdrew prematurely from the study will be assumed cured by Day7.

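### Keeping only the latest Day 7 assessment conflicts with the Day 10 limit, so an on-time report of cure or completed referral can be scored as a failure

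*SAP*

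**What the plan says.** SAP 6.1.1 provides for a child having more than one successful entry in the Day 7 or Day 28 database: "the most recent follow-up assessment within each database will be used". To limit recall bias it adds that "assessments conducted far beyond the expected follow-up time will be dropped", with the cut-offs "This will be 30 and 60 days from Day 0 for Day 7 and Day 28 respectively". It does not say which step comes first. It also notes: "Data collected as part of unscheduled visits are also integrated in these forms".

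For cure, SAP 6.1.2.8 sets a status condition and a date condition. On status: "A child will be counted in the numerator as cured if his/her status at the time of Day 7 follow-up is at home" and fully recovered. On date: "the follow-up date is within 7 days of Day 0, considering a + 3 days window", so Day 10 is the last admissible day. Children without Day 7 data are taken as cured.

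The same Day 10 limit applies to completed referral (6.1.2.6) and to the Day 7-form versions of scheduled and unscheduled follow-up (6.1.6). For these, missing Day 7 data count as not attended.

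For both primary outcomes, SAP 6.1.2.1 and 6.1.2.3 read the Day 7 assessment and turn to the Day 28 assessment only if the Day 7 one is missing. SAP 3.8 uses the date of death or admission regardless of when it was collected. Protocol 8.1.1 sets no window for the Day 7 contact, so late Day 7 forms are allowed.

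**The concern.** The Day 10 limit shows that the SAP wants an on-time report for these outcomes. The selection rule can discard that report in favour of a later one that fails the limit. The child then counts as a failure although a valid in-window success is in the database. Cure and completed referral are both listed secondary outcomes.

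The scoring is also inconsistent across children. One confirmed well twice can be scored not cured, while one never reached is scored cured.

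Nothing later in the SAP would reveal this. The sensitivity analyses in 6.2.4 do not vary the selection rule and concern only the primary outcomes. The missing-data methods in 6.3 address children lost or withdrawn, and these children are neither.

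**Working it through.** The plan states no figure here to reproduce, so the check applies the written rules to example sequences of Day 7-form entries.

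Inputs: latest entry kept and 30-day limit on Day 7 forms (SAP 6.1.1); cured only if well and dated by Day 10, and assumed cured if there are no Day 7 data (SAP 6.1.2.8). Because the order of selection and limit is not stated, both orders are shown. The last column uses the earliest assessment from Day 7 to Day 10, after the 30-day limit.

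| Day 7-form entries | SAP, select then apply limit | SAP, apply limit then select | Earliest in window |
|---|---|---|---|
| Day 8 well, Day 13 well | not cured | not cured | cured |
| Day 7 well, Day 14 well | not cured | not cured | cured |
| Day 7 well, Day 9 ill | not cured | not cured | cured |
| Day 7 ill, Day 9 well | cured | cured | not cured |
| Day 8 well, Day 32 well | no data, assumed cured | cured | cured |
| Day 8 ill, Day 32 well | no data, assumed cured | not cured | not cured |
| Day 4 ill, Day 7 well | cured | cured | cured |
| No entry | assumed cured | assumed cured | assumed cured |

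1. **Conflict with the Day 10 limit (rows 1 and 2).** Both reports agree that the child is well, yet the score is not cured under either order. The retained form is dated after Day 10.

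2. **Completed referral.** The logic is the same. A referred child whose hospital attendance is reported on Day 8, with a further entry on Day 13, fails the date condition and is scored as not completing.

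3. **Order of steps (rows 5 and 6).** If selection comes first, a Day 32 repeat is chosen and then dropped, leaving no Day 7 data although a Day 8 form exists. For cure this turns a recorded Day 8 illness into an assumed cure. If the limit comes first, the Day 8 form survives.

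4. **Changes of status within the window (rows 3 and 4).** The two rules differ in opposite directions. This is a choice of time point rather than an error, but it should be stated.

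5. **Primary outcomes.** If an admission is reported in a first Day 7 form and is absent from a later one, the later form is kept. The Day 7 assessment is then not missing, so 6.1.2.1 and 6.1.2.3 do not consult the Day 28 form. SAP 3.8 governs how an event is dated; it does not restore one held only in a discarded form.

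6. **Size for cure.** Let f be the share of children cured by a valid in-window call who also have a Day 7-form entry on Days 11 to 30. The fall in the cure proportion is f × cure rate. The documents do not give f. For the cure rate, 92% and 97% are borrowed from the background study in Protocol 3.2 as an illustration; they are not trial assumptions.

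| f | Fall at 92% cure | Fall at 97% cure |
|---|---|---|
| 1% | 0.01 × 92 = 0.92 points | 0.01 × 97 = 0.97 points |
| 5% | 0.05 × 92 = 4.60 points | 0.05 × 97 = 4.85 points |
| 10% | 0.10 × 92 = 9.20 points | 0.10 × 97 = 9.70 points |

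**The case against.** The best defence is that a second successful form should be rare. Under Protocol 6.5.1, further call attempts follow a failed first call. Protocol 8.2.2 names duplicate management as a cleaning task, with details in a Data Management Plan that is not available here. For dated events the latest report is also a reasonable choice: it can pick up an event after the first call or correct a mistaken first report. All of this limits the size of the problem, but it does not remove the conflict with the Day 10 limit.

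A reader might infer more than the documents support:

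- **That audit calls make repeats common.** Protocol 8.2.4 says that the Day 7 callers "will be audited through random checks of phone logs and repeat phone calls". It does not say that those calls enter the Day 7 database, and the SAP rule covers only what is recorded there.
- **That children are dropped.** The SAP drops assessments. The child stays in the all-recruited denominator. Losing a valid early form also depends on an order of steps that the SAP does not state.
- **That the rule always discards the assessment nearest Day 7.** Unscheduled-visit data enter the same forms, so an entry may precede Day 7. In the Day 4 and Day 7 example the rule keeps the nearer one.
- **That both primary outcomes are materially distorted.** Agreeing reports with dates leave them unchanged. Loss needs a later form that omits an event already reported. Protocol 6.5.1 does say that, after the initial call, "follow-up can be carried out with a caregiver other than the one who gave consent at the day of enrolment", but only if that person can inform about the child, and it gives no rate of disagreement.
- **That the comparison between arms is biased.** Protocol 7.2 has outcome data collected by phone by an assistant blinded to arm and facility, and no document suggests that repeats differ by arm. Equal repeats would mainly shift the level of the outcome.

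**Conclusion.** The point holds for the outcomes with a Day 10 limit: cure, completed referral and the Day 7-form follow-up outcomes. As written, a valid in-window success followed by a Day 7-form entry on Days 11 to 30 is scored as a failure, whichever order the steps take. The order of the 30/60-day limit and the selection is a separate ambiguity that can change a child's score.

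For the primary outcomes the exposure is smaller. It is confined to events reported only in a discarded Day 7 form, on the reading that 6.1.2.1 and 6.1.2.3 fix the order of sources.

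The overall size is unknown because the number of repeats is not given. The 0.9 to 1.0 points of cure per 1% of children affected rests on the borrowed 92 to 97% cure rates. The rule should be corrected before the final analysis because it gives a wrong result on its own terms and is easy to change.

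**What to change.** Amend SAP 6.1.1 as follows:

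- Apply the 30-day and 60-day limits to each assessment before any selection.
- For outcomes with the Day 10 limit, use the earliest successful assessment on or after Day 7 within the window.
- For death and hospitalisation, count an event reported in any valid assessment by its recorded date. Check conflicting reports against the hospital records already collected under Protocol 8.1.1.
- Report by arm the number of children with repeat assessments in each database.

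The cost is a few sentences of SAP text and a little more derivation code. No new data are needed.
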